## PROTOCOL SUMMARY

Study Title:	Median Lobe Prostatic UroLift Procedure
Study Objectives:	Evaluate the safety and effectiveness of the UroLift® System when used in symptomatic benign prostatic hyperplasia (BPH) subjects with an enlarged median lobe.
Study Design:	Prospective, multicenter, non-blinded, single arm (non-randomized) study.
Sample Size:	A total of no more than 48 subjects (minimum of 40) will be enrolled.
Subject Population:	Males age of 50 years or older diagnosed with symptomatic benign prostatic hyperplasia (BPH).
Number of Centers:	A maximum of 10 investigational sites located in the US
Clinical Indication:	The UroLift System is indicated for the procedure of symptoms due to urinary outflow obstruction secondary to benign prostatic hyperplasia (BPH) in men over the age of 50.
Effectiveness Endpoint:	At 6 months, the 95% lower confidence limit of the mean percent improvement in IPSS over baseline for the UroLift system must be $\geq 25\%$ . The Lower 95% confidence Limit, determined using bootstrap method is 50.8%.
Safety Endpoint:	The composite observed rate of post-procedure device related serious complications less than or equal to 15% at 3 months. Composite device related serious complications for this endpoint are 1) De Novo (new) severe urinary retention lasting more than 21 consecutive days post procedure, 2) Device related formation of fistula between the rectum and urethra, and 3) perforation of the rectum or GI tract, 4) damage to ureter or ureteral orifices 5) damage to the trigone requiring surgical repair or 6) de novo , sustained erectile dysfunction.
Additional Assessments:	Over the 12 month follow-up period, lower urinary tract symptoms (LUTS), quality of life (QOL), recovery, uroflowmetry, PVR, proportion of subjects who experience de novo sustained erectile dysfunction and anejaculation through 12 months, number of subjects with encrusted implants, patient satisfaction and adverse events severity and relatedness will be assessed.

## ENROLLMENT CRITERIA

### Inclusion Criteria

Subjects enrolled in this clinical study must meet all of the following criteria.

1. Male gender
2. Diagnosis of symptomatic BPH
3. Age  $\geq 50$  years
4. International Prostate Symptom Score (IPSS)  $\geq 13$
5. Peak urine flow rate  $\leq 12$  ml/sec on a voided volume  $\geq 125$  ml
6. Prostate volume  $\geq 30$  cc to  $\leq 80$  cc per ultrasound
7. Prostate Length measurement of  $\geq 30$  and  $\leq 80$  mm
8. Enlarged median lobe contributing to obstruction of the prostate

## Exclusion Criteria

Subjects will be excluded from the study if any of the following conditions apply.

1. Current urinary retention
2. Post void residual (PVR) urine > 250 mL
3. Active urinary tract infection at time of procedure
4. Previous BPH surgical procedure
5. Urethral conditions that may prevent insertion and delivery of device system into bladder (i.e. urethral strictures, meatal stenosis, bladder neck contracture)
6. Previous pelvic surgery (i.e. incontinence sling, trauma repair, penile implants, artificial sphincter) or irradiation
7. History of neurogenic or atonic bladder
8. Stress urinary incontinence
9. Biopsy of the prostate within the past 6 weeks
10. Life expectancy estimated to be less than 5 years
11. History of prostate or bladder cancer
12. Prostate-Specific Antigen (PSA) level above the age specific reference ranges, unless prostate cancer has been excluded to the satisfaction of the investigator.
13. Current gross hematuria
14. Known coagulopathies or subject on anticoagulants or antiplatelets other than aspirin  $\leq$  100 mg (unless antiplatelets are withheld minimum 3 days prior to procedure)
15. Use of the following medications pre-screening (uroflow, questionnaires)
  - Within 4 months of baseline assessment: estrogen, any drug producing androgen suppression, or anabolic steroids (excluding topical testosterone)
  - Within 3 months of baseline assessment: 5-alpha-reductase inhibitors
  - Within 2 weeks of baseline assessment:
    - alpha-blockers, androgens (topical are acceptable), gonadotropin-releasing hormonal analogs, anticholinergics or cholinergic medication
    - phenylephrine, pseudoephedrine, or imipramine medications
  - Within 1 week of baseline assessment, unless documented on stable dose for  $\geq$  6 months: beta blockers, antidepressants, anticonvulsants, and antispasmodics
16. Calculus urinary within the prior 3 months
17. Prostatitis requiring treatment (antibiotics) within the last year
18. Other co-morbidities that could impact the study results such as:
  - severe cardiac arrhythmias uncontrolled by medications or pacemaker
  - congestive heart failure NYHA III or IV
  - history of uncontrolled diabetes mellitus
  - significant respiratory disease in which hospitalization may be required
  - known immunosuppression (i.e. AIDS, post-transplant, undergoing chemotherapy)
19. Desire to maintain fertility post procedure
20. Unable or unwilling to complete all required questionnaires and follow up assessments (e.g. lives out of area)
21. Unable or unwilling to sign informed consent form
22. Currently enrolled in any other investigational clinical research trial that has not completed the primary endpoint.

## SCREENING ACTIVITY TIME PERIODS

Activity	Time Frame	Special Considerations
Flexible Cystoscopy	Within 6 months	Cystoscopy performed outside of study, within 6 months of index procedure, can be used to qualify for enrollment, provided eligibility morphology was determined, (enlarged median lobe.). If not all data collected with recording prior, there will also be a pre-procedure cystoscopy. This procedure, with video recording, will capture additional anatomical details and assist in implant planning.
TRUS or Pelvic Ultrasound	Within 6 months	Ultrasound performed outside of the study, within 6 months of screening, can be used to qualify enrollment, provided eligibility morphology (e.g. enlarged median lobe, Intravesical Prostatic Protrusion, etc.) and image are documented. In all cases, the image and data must be entered into EDC prior to index procedure.
Medical History	Within 30 days	
Uroflowmetry	Within 30 days	Either before cystoscopy or > 1wk after cystoscopy. Must be obtained after med washout
PVR	Within 30 days	Must be obtained after med washout
PSA	Within 6 months	
Urinalysis, Urine Culture & Sensitivity	Within 30 days	
Questionnaires	Within 30 days	Either before cystoscopy or > 1wk after cystoscopy. Must be obtained after med washout
Medications	Medication washout timeframe	Caveats
1) Estrogen, any drug producing androgen suppression, or anabolic steroids	1) 4 months prior to uroflow studies & questionnaires	
2) 5-alpha-reductase inhibitors	2) 3 months prior to uroflow studies & questionnaires	2) Subjects should remain off 5ARIs for the duration of the study, unless clinically required.
3) Alpha-blockers	3) 2 weeks prior to uroflow studies & questionnaires	3) Subjects should remain off alpha blockers for the duration of the study, unless clinically required.
4) Phenylephrine, pseudoephedrine, imipramine, anticholinergic or cholinergic medication	4) 2 weeks prior to uroflow studies & questionnaires	
5) Beta blockers, antidepressants, anticonvulsants, and antispasmodics	5) 1 week prior to questionnaires	5) Unless documented on stable dose for $\geq 6$ months, in which case the drug should not be altered or discontinued for entrance into or throughout the course of the study; unless otherwise deemed necessary for patient care.
6) Anticoagulants or antiplatelets other than aspirin <math>\leq 100</math> mg	6) 3 days prior to procedure	

## SUMMARY OF PROCEDURES

Tests and Assessments	Screening	Procedure Through Hospital Release	1 Month (± 7 days)	3 Months (± 14 days)	6 Months (± 30 days)	12 Months (± 30 days)
Questionnaires						
Urinary Symptoms	X		X	X	X	X
Sexual Function that includes MSHQ-EjD Sexual function, Anejaculation Function, IIEF	X		X	X	X	X
Incontinence Severity Index	X		X	X	X	X
Dysuria	X		X	X	X	X
Hematuria	X		X	X	X	X
Quality of Recovery VAS			X			
Pain VAS	X		X	X	X	X
Patient Satisfaction			X	X	X	X
Medical History	X		X	X	X	X
Sexual Function Assessment	X		X	X	X	X
Uroflowmetry 	X		X	X	X	X
PVR	X		X	X	X	X
PSA	X					
UA	X		X	X	X	
Urine Culture and Sensitivity	X		X	X	X	
TRUS or Pelvic Ultrasound 	X					
Flexible Cystoscopy 	X 	X 			X	
DRE		X 				
Catheterization		X	X	X		
Concomitant Medications	X	X	X 	X 	X 	X 
Adverse Events		X	X	X	X	X
Intervention Review		X	X	X	X	X

All subject Uroflow strip chart recordings, Ultrasound images and cystoscopy videos collected in the study will be forwarded to NeoTract

 Any cysto performed w/in 6 months can be used for screening if median lobe is identified. Index UroLift procedure to involve pre-procedure and post-procedure flexible cysto. Pre-procedure to record and confirm anatomy, plan implants; post-procedure to record outcome, ensure proper placement

 Performed to rule out rectum implantation

 Relevant medications only: BPH/LUTS; Sexual Function; GU; Prostate Cancer

## STATISTICAL ANALYSIS

### Primary Hypotheses

For the trial to be successful, the statistical evaluation of primary effectiveness endpoint must result in a rejection of the null hypothesis (H0) in favor of the alternative hypothesis (H1).

**Primary Effectiveness Endpoint:** UroLift system compared to an Objective Performance Goal (OPG) at 6 months post treatment:

Let  $\delta\mu_p$  equal the expected percent change in IPSS scores from baseline at 6 months. The null and alternative hypotheses are as follows:

$$H_0: \delta\mu_p \leq 25\%$$

$$H_1: \delta\mu_p \geq 25\%$$

## Sample Size Estimate

From a practical perspective, the sample size estimate can be based on the number of expected subjects that could have been included in the UroLift pivotal trial (L.I.F.T.) had subjects with median lobe been allowed to enroll. To statistically corroborate the sample size estimate, an evaluation of the IPSS response in the L.I.F.T. treatment arm at 6 months was evaluated. Taking this value and applying a lower confidence bound, the estimated mean IPSS response for this study was determined.

For a one-sided 95% confidence interval, based on a t-test, the sample size estimate was calculated.

## Intention to Treat Group

The main analyses, including endpoints, will be performed on the “intent-to-treat (ITT)” group. All subjects who are enrolled will be included in the intention to treat analysis. With the ITT analysis, primary outcome data from subjects retreated with either the UroLift System or with any other surgical procedure will be censored the day after the alternative procedure. Additionally, subjects that start on alpha blockers or 5ARI medications specifically for the treatment of BPH, and use then consistently will have their results censored the day after starting this medication. Consistent usage is defined any medication use for more than 60 days.

The IIT population is used for efficacy analyses.

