## Evaluation of Primary Effectiveness Hypothesis

If the lower limit of the one-sided 95% confidence interval for mean IPSS percentage change for the UroLift system at 6 months is greater than or equal to 25%, then the null hypothesis will be rejected in favor of the alternative hypothesis. (The lower 95% confidence limit, determined using bootstrap method is 50.8%.)

Subjects who have missing IPSS data due to lost to follow-up will have the percent change from baseline at 6 months value imputed using the MCMC (Markov Chain Monte Carlo) multiple imputation method. Partially completed IPSS questionnaires will also be considered missing. The lower bound of the one-sided 95% confidence interval will be constructed using the mean and standard error from the MCMC method.

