## Analysis of Success Measures

For subjects treated with the UroLift System, the procedure will be considered successful if the post-procedure cystoscopy exhibits an increase in the urethral opening post-procedure and the subject is free of device/procedure related serious adverse events immediately post-procedure. Independent of whether or not the procedure was successful, all subjects will be included in the ITT analysis of the primary endpoints.

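### The plan does not say what a man censored after retreatment or sustained BPH medication contributes to the 6-month IPSS mean; the rule should be fixed in advance

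*Combined protocol and SAP*

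**What the plan says.** Under Primary Hypotheses, the quantity tested is "the expected percent change in IPSS scores from baseline at 6 months", compared with a fixed goal of 25%. The trial passes if the one-sided 95% lower limit reaches that goal.

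The Intention to Treat Group section says: "All subjects who are enrolled will be included in the intention to treat analysis". On the primary data it then states that "subjects retreated with either the UroLift System or with any other surgical procedure will be censored the day after the alternative procedure". Men who start an alpha-blocker or 5ARI for BPH and use it consistently "will have their results censored the day after starting this medication". The threshold is given as: "Consistent usage is defined any medication use for more than 60 days".

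The section Evaluation of Primary Effectiveness Hypothesis sets the missing-data rule: "Subjects who have missing IPSS data due to lost to follow-up will have the percent change from baseline at 6 months value imputed", by MCMC multiple imputation. It adds: "Partially completed IPSS questionnaires will also be considered missing". The lower bound is built from the MCMC mean and standard error. The variables in the imputation model are not listed.

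Analysis of Success Measures repeats the inclusion rule: "Independent of whether or not the procedure was successful, all subjects will be included in the ITT analysis of the primary endpoints".

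The Summary of Procedures schedules the urinary-symptom questionnaire at screening and at 1, 3, 6 and 12 months.

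**The concern.** Censoring has a ready meaning in a time-to-event analysis. In a mean at a fixed visit it only removes a score and does not say what replaces it. A man retreated at month 4 who attends at month 6 is neither lost to follow-up nor a partial completer, so the imputation rule does not reach him. Yet he must be included. No section reconciles these statements.

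The men affected are those for whom the device did not suffice. If their scores are left out, or imputed from a model without their earlier scores, their place is in effect taken by the experience of men who did not need retreatment. There is no control arm in which the same handling would offset this. Without a stated rule, the choice could be made after the data are seen, and the reported mean and lower bound can differ by several points according to that choice.

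**Working it through.** **Inputs from the documents.** Goal 25%; one-sided 95% limit; 40 to 48 men; single arm; lower limit of 50.8% by bootstrap, stated in the Protocol Summary and in Evaluation of Primary Effectiveness Hypothesis.

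**Inputs the documents do not give.** SD, failure rate, correlation between visits, planning mean and power. The sample size therefore cannot be reproduced, and the 50.8% comes without a mean, SD or n. Every value below for those quantities is an assumption.

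**1. Shift of the mean, exclusion against scoring 0%.** With k of N men censored and the others averaging m, exclusion gives m and scoring 0% gives m(N - k)/N. The difference is (k/N) × m.
- 10% failures, m = 50%: 0.10 × 50 = +5.0 points.
- k = 4, N = 48: 2.9 points if m = 35%; 4.2 points if m = 50%.

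Imputation without earlier scores has the same expected shift, because it draws from the distribution of the other men.

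**2. Shift of the mean, imputation with earlier scores.** Let f be the failure fraction, μ the other men's mean (taken as the same at both visits, with equal SD), ρ the correlation of the pre-event score with month 6, and p the failures' mean pre-event improvement. The shift against scoring 0% is f × [μ(1 - ρ) + ρp]. With f = 0.10 and μ = 50%:
- ρ = 0.8, p = -20%: 0.10 × (10 - 16) = -0.6 points.
- ρ = 0.6, p = +15%: 0.10 × (20 + 9) = +2.9 points.
- Only the 1-month score usable (event before the 3-month visit), ρ = 0.4: 0.10 × (30 - 8) = +2.2 to 0.10 × (30 + 6) = +3.6 points.

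**3. Effect on a lower limit near the goal.** N = 48, k = 4, others' mean 35%, SD 35.
- Excluded: 35 - 1.681 × 35/√44 = 26.1%, goal met.
- Scored 0%: mean 44 × 35/48 = 32.1%; SD over all 48 is 34.9; 32.1 - 1.678 × 34.9/√48 = 23.6%, goal missed.

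The first reversal for these inputs is at k = 3. With N = 40 it is at k = 1 (25.6% against 24.8%). With a mean of 40%, it takes 6 to 10 men (SD 25-35, N 40-48); with 50%, 13 to 17.

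**4. False success at a true mean of 25%.** Failures 10%, truly at 0%, so the others average 25/0.9 = 27.8%. Under exclusion the test sees an excess of 2.8 points. The approximate pass probability is 1 - Φ(1.645 - 2.78/(SD/√(0.9n))):
- n = 40, SD 40: 1 - Φ(1.645 - 0.417) = 11.0%.
- n = 48, SD 30: 1 - Φ(1.645 - 0.609) = 15.0%.

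Simulation over n = 40-48 and SD 30-40:

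| Handling of censored men | False success |
|---|---|
| Scored 0% | about 4-5% |
| Excluded | about 10-15% |
| Imputed, ρ 0.6-0.8, p = -20% | 3.1-5.5% |
| Imputed, ρ 0.6-0.8, p = 0% | 5.8-8.6% |
| Imputed, ρ 0.6-0.8, p = +15% | 8.0-12.0% |

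**5. If 50.8% is representative.** Suppose it is the limit with 4 men excluded. Scoring them 0% lowers it to 44.2-45.6% (SD 25-35, N 40-48). It would take 17 to 22 such men to bring it below 25%.

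**The case against.** The strongest reply is that the plan, read as a whole, does not exclude anyone. All enrolled men are included, and the bound comes from the MCMC analysis, so the natural meaning is that a censored score is missing and is imputed. On that reading the exclusion figures do not apply, and with earlier scores in the model the shift is small and can be negative. This stands in part. Exclusion is the reading that the inclusion wording least supports. But the imputation rule limits itself to loss to follow-up and partial questionnaires, and does not say that earlier scores enter the model. The intended reading has to be supplied by the reader.

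A second reply is that almost any rule gives a higher mean than assigning 0%, so the direction depends on the reference chosen. That is right. A reader might infer that 0% is the correct value for these men and that the censoring rule is an error. The documents do not support this: censoring after retreatment is a choice of what to estimate. Against scores observed after retreatment, exclusion need not favour the device: with 10% failures and others averaging 50%, it shifts the mean by 0 if those scores average 50%, and by 0.10 × (50 - 65) = -1.5 points if they average 65%.

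A third reply is that the only effect figure in the plan, 50.8%, lies far above the goal. Its source is not explained, but if it is representative this removes most of the risk to the verdict.

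**Conclusion.** The gap is real: no section gives a censored man a value in the 6-month mean, and a literal application lets treatment failures drop out. Under the assumptions shown, the choice is worth up to about 5 points on the mean if failures are excluded, and -0.6 to +2.9 points if they are imputed with earlier scores correlated 0.6-0.8 with month 6. The error rate rises materially above 5% under exclusion, but only for a true mean at or near 25%.

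A reader might go further and infer that the trial's pass is in doubt, or that the sponsor planned to discard failures. Neither follows. The inclusion statements point away from discarding, and a limit near 50.8% would survive any plausible handling of a few men. What moves in that case is the reported effect, not the verdict. The number of men affected is not given, and only those retreated or started on qualifying medication before their 6-month IPSS matter. The point should be fixed, with medium confidence in its size.

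**What to change.** In the Intention to Treat Group section and in Evaluation of Primary Effectiveness Hypothesis, state that a 6-month IPSS censored under the retreatment or medication rule is treated as missing and imputed by the same MCMC model as other missing scores. Name baseline, 1-month and 3-month IPSS as model variables, using pre-event values only for censored men. All enrolled men then contribute to the mean and lower bound. Leave the 60-day definition as it is.

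Pre-specify two sensitivity analyses, reported beside the primary result:
1. Count these men as non-responders at 0% improvement, with a variant that uses the last pre-event change if that is worse.
2. Use observed scores regardless of retreatment or drug, where available.

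The first is needed because imputation does not fully restore the error rate if failures are held to be at 0% (up to 12.0% in the table above), and helps less when only a 1-month score precedes the event. It should not replace the primary rule: that would change what is estimated, and the worse-of variant can cost up to 38 points of pass probability against exclusion at a true mean of 40% (assumed 10% failures whose last score averaged -20%).

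The cost is SAP wording, a little more analysis, and a somewhat lower effect in the failure-scored analysis. The scores needed for the imputation model are already scheduled. The second sensitivity analysis depends on retreated men still completing the IPSS, which the documents do not state.

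### Drug censoring depends on why an alpha-blocker or 5ARI was started, so an on-drug 6-month IPSS under another stated reason stays in the primary mean

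*Combined protocol and SAP*

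**What the plan says.** The primary analysis compares the "lower limit of the one-sided 95% confidence interval for mean IPSS percentage change" at 6 months with a goal of 25% (Evaluation of Primary Effectiveness Hypothesis).

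The drug rule, under Intention to Treat Group, is that "subjects that start on alpha blockers or 5ARI medications specifically for the treatment of BPH, and use then consistently will have their results censored". It has two conditions that must both hold. The first is class and reason, as just quoted. The second is duration: "Consistent usage is defined any medication use for more than 60 days".

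Elsewhere the plan treats the two classes by exposure. Exclusion criterion 15 and the medication rows of Screening Activity Time Periods require 3 months off 5ARIs and 2 weeks off alpha-blockers before baseline, with no mention of why the drug was taken. For follow-up, the same rows say "Subjects should remain off alpha blockers for the duration of the study, unless clinically required" and "Subjects should remain off 5ARIs for the duration of the study, unless clinically required". Neither exception is limited to BPH, and neither says what happens to the score.

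Follow-up medication recording is restricted in footnote 4 of Summary of Procedures: "Relevant medications only: BPH/LUTS; Sexual Function; GU; Prostate Cancer".

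Multiple imputation is specified for men lost to follow-up, and partly completed questionnaires count as missing. The plan does not say how a censored 6-month value enters the mean. It contains no sensitivity analysis for drug use.

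**The concern.** These drugs are washed out because they can affect the IPSS, and that does not depend on the reason for the prescription. Baseline is kept free of them by exposure, whereas the 6-month value is kept free of them only by stated reason. With no control arm, any IPSS gain from the drug is credited to the device against a fixed goal.

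The word *specifically* also needs interpretation. An alpha-blocker taken for more than 60 days for post-procedure retention in a man enrolled with symptomatic BPH could be classed either way. The plan names nobody to decide; the CEC's stated task concerns the safety endpoint. In a non-blinded study that decision could be made with the outcome known.

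At stake is a modest upward bias in the primary mean, and how well the censoring can be defended.

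**Working it through.** **1. What the rule catches.** Use of either class for more than 60 days, sorted by stated reason:

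| Stated reason | Censored as written? | Recorded at follow-up (footnote 4)? |
|---|---|---|
| BPH | Yes | Yes |
| Post-procedure retention, catheter weaning | Depends on how *specifically* is read | Probably, as GU or BPH/LUTS |
| Stone, haematuria | Not on a literal reading | Probably, as GU |
| Blood pressure, hair loss | No | Possibly not |

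**2. Inputs.** From the documents: n = 40 to 48 enrolled, goal 25%, one-sided 95% limit, printed lower limit 50.8%. Assumed, because the documents give no figure: the number k of on-drug men left in, the drug's added improvement d in percentage points, and the SD of percent change. The plan has no figure of its own for drug contamination to reproduce. The sample size cannot be reproduced either, since its expected mean, SD and power are not given; n serves here only as a divisor.

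**3. Shift in the mean** = k × d / n, for d = 10 to 30.
- One man, n = 40: 10/40 = 0.25 to 30/40 = 0.75 points.
- One man, n = 48: 10/48 = 0.21 to 30/48 = 0.625 points.
- Three men, n = 40: 30/40 = 0.75 to 90/40 = 2.25 points.

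**4. Error rate at the boundary.** Data were simulated with a true device mean of exactly 25%, a t-based lower limit and 60,000 runs per setting, over SD 25 to 45, n = 40 and 48, and a higher assumed range of d = 20 to 50.
- No on-drug man: 0.050 to 0.051 (nominal 0.05).
- One on-drug man: 0.056 to 0.080.
- Two on-drug men: 0.064 to 0.119.

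**5. Against the printed limit.** The gap is 50.8 − 25 = 25.8 points. With the standard error held fixed, closing it needs k = 25.8 × n / d. At d = 50 this is 25.8 × 40 / 50 = 20.6, so 21 of 40 men, or 25.8 × 48 / 50 = 24.8, so 25 of 48. At d = 30 it is 25.8 × 40 / 30 = 34.4, so 35 of 40.

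**6. Does dropping the score remove the bias?** Suppose the other men average m, and this man would score y off drug and y + d on drug. Keeping him biases the mean by d/n; dropping him biases it by (m − y)/n. Dropping is worse whenever y + d < m. Two illustrations with assumed values, 39 men at 50%:
- *Poor responder, 10% off drug and 30% on drug.* True mean (39 × 50 + 10)/40 = 49.0; kept (39 × 50 + 30)/40 = 49.5; dropped 50.0. Dropping doubles the error.
- *Average responder, 50% off drug and 70% on drug.* True mean 50.0; kept (39 × 50 + 70)/40 = 50.5; dropped 50.0. Dropping removes the error.

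The handling of censored scores therefore has to be settled together with the trigger.

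**The case against.** The strongest objection is to the simple remedy. Deleting the reason clause alone, with censored scores left undefined, could push the mean further up for a poor responder (step 6). This stands, and the fix below is built around it.

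A reader might also infer that the leak systematically favours the device, because the men left in are those in whom it worked least. The documents do not support that. Every man is enrolled with symptomatic BPH, so long-term alpha-blocker use for poor voiding may well be classed as BPH treatment and already censored. The clearly uncovered uses, such as blood pressure or hair loss, have no stated link to poor device response. For those uses only the drug effect itself remains.

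Nor do the documents show that the wording on a site's prescription decides inclusion. They do not say who classifies the reason or from what record.

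A contrast with surgery is tempting, since men "retreated with either the UroLift System or with any other surgical procedure will be censored the day after the alternative procedure" with no explicit test of reason. It is weak: retreatment and an alternative procedure already imply BPH treatment.

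It is fair to say that the instruction to stay off both classes should make such use uncommon, and that footnote 4 probably captures use for retention, stones or haematuria. Both narrow the gap without closing it. Censoring only alternative BPH therapy is a coherent target in itself, but it fits poorly with a baseline washout that disregards reason.

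**Conclusion.** The gap is real. As written, a BPH reason is necessary for censoring, and nothing else in the plan deals with the on-drug 6-month score of a man treated for another reason. The likely effect is small: 0.25 to 0.75 points per man at n = 40 under an assumed drug effect of 10 to 30 points, with the number of men unknown.

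A reader might infer that trial success is in doubt. The documents do not support that. If 50.8% is the trial's own lower limit, more than half of the men would have to be on drug even at an assumed 50-point effect. The documents do not say whether that figure is a result or a planning value. The error rates in step 4 apply only at a true mean of exactly 25%.

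This is an inexpensive improvement to the estimate and to its defensibility. It is separate from the 60-day threshold, which leaves shorter BPH-labelled courses uncensored as well.

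**What to change.** - **Intention to Treat Group:** delete the reason clause, so that the analysis rule depends on exposure to either class. List the indication, but do not let it decide inclusion.
- **Summary of Procedures, footnote 4:** record alpha-blockers and 5ARIs at follow-up for any indication.
- **Evaluation of Primary Effectiveness Hypothesis:** state that 6-month scores censored under this rule are not dropped but are multiply imputed, with a model that includes baseline IPSS and the IPSS from visits before the drug was started. This rests on the usual missing-at-random assumption, and a man who starts early will have little pre-drug information, so the assumption should be stated.
- **Sensitivity analysis:** repeat the primary analysis with the observed on-drug scores kept.

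The cost is a few sentences in the SAP and one CRF instruction. The downside is a few more imputed 6-month scores, slightly wider limits, and a mean that may move slightly in either direction. The change affects analysis and data capture only, not clinical management.

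### A 6-month IPSS recorded during an alpha-blocker or 5ARI course of 60 days or less stays in the primary mean, although baseline IPSS must be taken after washout

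*Combined protocol and SAP*

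**What the plan says.** **Baseline.** Exclusion criterion 15 rules out recent use of BPH drugs. For 5ARIs it reads "Within 3 months of baseline assessment: 5-alpha-reductase inhibitors". The medication rows of Screening Activity Time Periods set the alpha-blocker interval at "2 weeks prior to uroflow studies & questionnaires", and the questionnaire row of that table states "Must be obtained after med washout".

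**After the procedure.** The same table asks subjects to stay off both classes but permits use where there is a clinical need. No washout is required before the 6-month questionnaire.

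**Analysis rule.** The Intention to Treat Group section covers "subjects that start on alpha blockers or 5ARI medications specifically for the treatment of BPH". Those who take them consistently "will have their results censored the day after starting this medication". The threshold is given as "Consistent usage is defined any medication use for more than 60 days". The section does not say whether duration is judged at the visit or over the whole course, or whether days are consecutive or cumulative.

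**Endpoint.** Evaluation of Primary Effectiveness Hypothesis requires the lower one-sided 95% limit of the mean percent change in IPSS at 6 months to be at least 25%. It describes multiple imputation for loss to follow-up and treats partial questionnaires as missing. It does not say how a medication-censored value enters the mean.

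**The concern.** Percent change compares two scores, and here the two can be taken under different drug conditions. At baseline, alpha-blocker use within the previous two weeks makes the score unacceptable. At 6 months, a man currently taking the drug can contribute a score if his course is short enough. The plan accepts in principle that a score obtained with drug help is not device effect, since it censors longer use. The weakness is that the trigger is duration of use and not drug status when the endpoint is measured.

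The study is single-arm and non-blinded with a fixed goal, so no control group offsets a drug contribution. Any drug benefit in a retained score moves the mean towards passing.

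The unstated timing adds a second problem. If duration is judged over the whole course, whether a 6-month score counts depends on drug use after that score was recorded. If it is judged at the visit, every start in the preceding 60 days is retained.

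**Working it through.** **The plan's own figures.** No figure in the plan bears directly on this rule. The sample size of 40 to 48 cannot be reproduced because the expected mean, SD and power are not given. The 50.8% lower limit is printed without its source data.

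**Step 1: which courses escape the rule.** Take the visit at day 180 (assumed) and count the start day as day 1 of use. A course of at most 60 days that includes the visit starts no earlier than 180 − 59 = day 121 and no later than day 180. At the edges of the ±30-day window the ranges are days 91-150 (visit at day 150) and days 151-210 (visit at day 210).

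- Course ends by its 60th day: the score is kept under either reading of the rule.
- Course exceeds 60 days, duration judged over the whole course: the score is censored back to the day after starting.
- Course exceeds 60 days in the end, but not by the visit, duration judged at the visit: the score is kept.

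**Step 2: shift in the mean.** Shift = k × d / n, where k is the number of affected men, d the drug contribution in percentage points and n the number analysed. The range for n comes from the Protocol Summary; k = 2 to 4 and d = 10 to 30 are assumptions.

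- Low: 2 × 10 / 48 = 0.42 points.
- High: 4 × 30 / 40 = 3.0 points.

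This puts 2/48 = 4% to 4/40 = 10% of subjects on a short course over one visit.

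**Step 3: effect on the one-sided error.** With SD 35 and n = 44 (both assumed), SE = 35/√44 = 5.3. If the true off-drug mean is exactly 25%, the chance of passing is P(Z > 1.645 − shift/5.3).

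| Shift (points) | Chance of passing |
|---|---|
| 0 | 5% |
| 0.42 | about 5.9% |
| 1 | about 7% |
| 3 | about 14% |

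A noncentral-t calculation with n = 40 to 48 and SD 30 to 40 gives about 6% at 0.5 points and 12-17% at 3 points.

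**Step 4: distance from the goal.** If the lower limit were 50.8%, it would have to fall by 50.8 − 25 = 25.8 points to change the decision. At a constant SE and a 30-point drug contribution, that needs 25.8/30 = 86% of subjects on drug.

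**Step 5: does removing these scores reduce the bias?** Not automatically. Illustration with assumed inputs: n = 44, true off-drug mean 25% (total 44 × 25 = 1100), and three men with zero off-drug improvement and a 20-point drug effect.

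- Current rule: (1100 + 3 × 20)/44 = 26.4%, a bias of +1.4.
- Three men dropped: 1100/41 = 26.8%, a bias of +1.8.

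Dropping poor responders can therefore be worse than keeping their on-drug scores. The replacement value has to come from each man's own pre-drug data.

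**The case against.** A reader might infer that on-drug 6-month scores generally count as device effect. The documents do not support that. Once use exceeds 60 days, results are censored from the day after starting, so if duration is judged over the whole course, a man who started the week before the visit and stayed on the drug loses his score. The instruction to stay off both classes reduces the numbers further. What certainly remains is a course for BPH that covers the visit and ends within 60 days.

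A reader might also infer that the retained men are the device failures. That describes persistent users better, and the rule is aimed at them. Nothing in the documents shows that men with short courses responded poorly.

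It can fairly be said, too, that the number of men, the drug effect and the SD are all assumed, that the error rates apply only at a true mean of 25%, and that sending these men into an undefined category of censored subjects could raise the estimate (Step 5).

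These objections limit the size of the point and shape the remedy. They do not close the gap: no section requires washout before the 6-month IPSS, and none provides a rule or sensitivity analysis for a score recorded during a shorter course.

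**Conclusion.** The concern holds in a narrow form. The 60-day threshold leaves on-drug scores from short courses in the primary mean, in conflict with the off-drug condition imposed at baseline, and the rule does not state when duration is judged.

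The size is unknown from the documents. Under the assumptions in Steps 2 and 3, the mean rises by 0.4 to 3 points and the one-sided error at the 25% boundary goes from 5% to about 6-14%. This matters only if the result lies close to the goal. It would be too strong to conclude that the trial's pass decision is in doubt: with a lower limit near 50.8%, the decision would stand, though the reported effect could still be somewhat inflated. The rule should be corrected because it is inconsistent and the correction is cheap, not because a large bias has been shown.

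**What to change.** Change the analysis rule only; patient care is unaffected.

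1. Define the trigger by drug status at the endpoint: a 6-month IPSS recorded while the subject is taking an alpha-blocker or 5ARI for BPH is not used as device effect, whatever the total days of use.
2. State how the value is replaced: by multiple imputation conditioned on the subject's own baseline IPSS and his pre-drug 1- and 3-month IPSS. He is not dropped from the analysis.
3. Report three sensitivity analyses: (a) keep the 60-day rule, stating when duration is judged and whether days are consecutive or cumulative; (b) carry forward the last pre-drug IPSS, or set improvement to zero; (c) extend the trigger to the plan's own baseline washout intervals for each class.

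The pre-drug scores should usually exist. With 3 months taken as day 90, that visit falls by day 90 + 14 = 104, before the earliest start of day 121 in Step 1 for a visit at day 180. Analysis (b) covers men who worsened after their last pre-drug score.

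The cost is a few sentences in the analysis plan. IPSS and BPH/LUTS medications are already collected at every follow-up visit; the sponsor should confirm that drug start and stop dates are captured. The downside is slightly more imputation, and the estimate may move in either direction.
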